The MRI-based assessment of muscle volume for validation of the HMF technique is analyzed independently from the strength training intervention. Thereby, the accuracy of the HMF technique is dependent on the initial generic musculoskeletal model that is used for model fitting, as well as the available subject-specific skin surface and anthropometric data. The level of significance in the difference of muscle volume between HMF and MRI is expected to vary across muscle-tendon groups, as well as between population groups and gender. In particular, no significant differences were found in the predicted volume of semitendinosus and semimembranosus as part of the hamstrings between HMF and MRI in 5 children without CP (MRI 5.1 (0.91) versus HMF 5.0 (0.30)  $\text{cm}^3/\text{kg}$ ,  $p\text{-value} > 0.05$ ) and in the predicted volume of the quadriceps, including vastus lateralis, medialis, intermedius and rectus femoris, in 6 children with CP (MRI 15.9 (3.20) versus HMF 16.5 (2.58)  $\text{cm}^3/\text{kg}$ ,  $p\text{-value} > 0.05$ ), respectively [22]. Based on previous research, it can be expected that additional consideration of somatotype from anthropometric measurements will help to improve model fit by allowing to adjust the relative thickness of the skin layer, and thus segmental inertia properties, via the HMF objective function for individual subjects. Furthermore, it is very likely that the accuracy in fitting results will be improved when fitting a generic musculoskeletal model to subjects of similar age and gender, and without significant musculoskeletal impairments, which will be the case in the present study. Further details to the MRI-based analysis are provided in Subsection 3.3.

All participants have to confirm their voluntary participation with a written informed consent before being submitted to any study procedure.

Inclusion criteria (all participants,  $n=36$ ):

- Healthy participants; and
- Age 18-40 years old; and
- No acute or chronic musculoskeletal symptoms or pain; and
- Experience with strength training (at least 1-year strength training experience with one training session per week or more); and
- Familiar with strength exercises of key muscles associated with knee joint stability.

Exclusion criteria (all participants,  $n=36$ ):

- Acute or chronic musculoskeletal pain; and/or
- Musculoskeletal surgery within the last 12 months; and/or
- Ongoing rehabilitation or treatment of musculoskeletal complaints or injury; and/or

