- **3rd Visit:** The same measurements as at baseline (2nd Visit) will be taken after the strength training intervention, following the same protocols so that the key outcome parameters can be compared before/after training. The approximate duration of the 2nd Visit is **4h**. The 3rd visit is defined within 7 days following the 8-week strength training intervention.

All the procedures in this study are standard procedures in athlete performance monitoring and musculoskeletal health & sports science. 3D body surface data are taken with the participant standing in neutral standing position using a structured light body surface scanner at the ZHAW, taking only a few seconds with extremely high accuracy between the scanned and the actual body volume without requiring any physical contact [37]. Strong in-house support is provided by the department of physiotherapy, at the ZHAW for access and expertise with isokinetic tests, ultrasound and anthropometric measurements according to ISAK standards. Kinematic data will be recorded simultaneously from the iPhone/watchOS and synchronised to a 3D motion capture system (10 camera Vicon System, Oxford Metrics Group, UK). A laptop is used that connects via Bluetooth with the mobile measurement devices, and has the required software for data acquisition and analysis [33]. The set of exercises are standard exercises for strength training, and instructions are given according to established guidelines (see Table 3.3.2). The order of exercises and 3-minute rest interval between exercises are defined to minimise the effects of muscular fatigue on the study results.

MRI scans from pelvis to the toe with the participants lying supine with straight legs are done at the SCMI with support from a professional radiographer (facilities, including technical support are booked by hour) in line with previous research by our group [21] (Scan parameters: TR-TR-3690 ms, TE-67 ms, Slice thickness 4 mm, base resolution 320, gap between slices 10 mm, approximately 70 pictures, 6.5 s per picture). The total scan time is approximately 10-15 min. The chosen values of 4 mm for slices thickness and 10 mm gap between slices are the minimum number of images possible to ensure sufficient images for deriving subject-specific muscle-tendon lengths and volumes of each participant.

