	Warm up	Preparation for strength assessment and kinematic data acquisition	Participant performing individual warm up of 5-10 minutes on rower or bike.
	Isokinetic tests	Isokinetic tests according to established protocols at the Swiss Olympic Medical Centre.	Participants performs the standard isokinetic test for hamstring and quadriceps on a commercial testing machine.
	Functional calibration	Measurement set-up and conduct of functional calibration and synchronisation of Apple Watch, iPhone and Vicon system.	Participant to stand upright in relaxed neutral position for attachment of reflective skin markers and Apple watch. Participant to perform set of standard movements for functional calibration.
	Exercises for the assessment of strength- and training-specific data	Forward lunges	Participant to stand upright and move into a lunge position with the front leg. Keep back straight and head upright. Initiate upward movement before the rear knee touches the ground [43].
		Side lunges	Participant to stand upright and move into a side lunge position. Keep back straight and head upright. Shift weight back into neutral standing position and alternate to other side.
		Squat	Participant to stand upright with feet hip-width apart and slightly pointing out. Make sure not to bend forward but keep back straight and knees pointing out in direction of toes.
		Drop jumps	Participants jump from a 30cm box onto the ground and stand still after landing [41].
		Counter-movement jumps	Participant to stand upright, dynamically move into a squat position followed by a vertical jump as high as possible.
		Side-step cutting movements	Participants sprints forward and changes the direction with a cutting side step to the left respectively the right side.
	Dismissal	Participant is shown preliminary results and is informed about further research process.	Participant is given time to look at data and ask questions. Outlining of further study process and thank you for participation.
4rd Visit: MRI of the lower limbs (n=12)			

0.5 h	Welcome	Outline procedure and double-check inclusion/exclusion criteria. Pregnancy test for female participants. Withdraw participant if health situation has changed.	Confirm inclusion/exclusion criteria and time for questions.

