## **6.2 Risk-Benefit Assessment**

The overall risk for participants is minimal, with the risk of harm due to the procedure itself being minimized by the design of the protocol. All the methods and techniques that are used for data collection are non-invasive and based on standard protocols in athlete performance monitoring and musculoskeletal health & sports science.

The training routine of each participant will be discussed and only participants who are familiar with the proposed set of strength exercises will be included. The strength exercises are identical with the exercises that are being performed in usual fitness and rehabilitation routines. The risk of musculoskeletal injury is equivalent to the risk during their standard strength training routine. IMU measurements and optical motion capture require small reflective markers or devices (watchOS) to be attached to the body surface. Possible skin irritations are very rare and can be locally treated (creams).

Only a sub-group of  $n=12$  participants is recruited for MRI of the lower limbs. This is because MRI is costly and MRI-based subject-specific musculoskeletal modelling is very time consuming. There are minimal additional risks and time burden (i.e. 0.5h) for participants who are undergoing MRI. MRI is the gold standard technique for musculoskeletal imaging without exposing the subject to harmful radiation [38]. In case a participant feels uncomfortable inside the MRI tunnel due to claustrophobia or other reasons, the imaging can be discontinued anytime. The same holds for 3D body surface scanning, ultrasound, isokinetic strength tests and marker-based optical motion capture, should a participant feel uncomfortable or exhausted. Participants will be offered to rest at the research and training facilities of the ZHAW during and after different types of measurements to minimize risk of fatigue or injury.

The risk of unauthorized data access and/or unwanted identification of project participants is minimized through ensuring safe data recording and storage procedures (as detailed in Section 7). The health- and training-related questionnaire is not known to be related to any risks as it does not include any psychiatric questions that could traumatize.

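### Three of the six exercises at Visits 2 and 3 are jump, landing or cutting tasks, but the familiarity criterion and the injury-risk comparison are written for strength exercises only

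*Combined protocol and SAP*

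**What the plan says.** Section 3.3, Table 3.3.3 lists six exercises for Visits 2 and 3 under the label "Exercises for the assessment of strength- and training-specific data". They are forward lunges, side lunges, squat, drop jumps, counter-movement jumps and side-step cutting. The instructions for the last three are:

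- Drop jumps: "Participants jump from a 30cm box onto the ground and stand still after landing".
- Counter-movement jumps: from standing, "dynamically move into a squat position followed by a vertical jump as high as possible".
- Side-step cutting: "Participants sprints forward and changes the direction with a cutting side step to the left respectively the right side".

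Three other places describe these exercises or set the safeguard for them:

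- The text of section 3.3 states: "The set of exercises are standard exercises for strength training".
- The last inclusion criterion in section 3.1 reads: "Familiar with strength exercises of key muscles associated with knee joint stability".
- Section 6.2 says each participant's training routine will be discussed and that "only participants who are familiar with the proposed set of strength exercises will be included". Two sentences later it concludes: "The risk of musculoskeletal injury is equivalent to the risk during their standard strength training routine".

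**The concern.** Section 6.2 argues that participants already do these exercises, so the study adds no injury risk beyond their own training. That argument works for a squat in someone with a year of strength training. It does not carry over by itself to landing from a box, jumping for maximal height, or sprinting and cutting. A person whose only training is in a gym meets every written criterion and would be asked to do all three.

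What is at stake is participant protection and the accuracy of the risk statement. Section 1.5 claims the minimal-risk category, and sections 1.5 and 6.2 both support that claim by pointing to strength exercises that participants would do anyway. If half of the visit exercises fall outside that description, the stated argument is incomplete for them, whatever their actual risk turns out to be.

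**Working it through.** The plan gives no figure on this point to reproduce. The check is a count followed by a comparison of the passages.

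**Step 1: count the tasks (Table 3.3.3).**

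| Visit exercise | Jump, landing or cutting? | Named in the section 2.3 exercise list? |
|---|---|---|
| Forward lunges | No | No |
| Side lunges | No | No |
| Squat | No | Yes |
| Drop jumps (30 cm box) | Yes | No |
| Counter-movement jumps | Yes | No |
| Side-step cutting | Yes | No |

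Share of the exercise block: 3 / 6 = 50%. This is half of the exercises, not half of the visit, which also includes anthropometry, a 3D scan, ultrasound, isokinetic tests and functional calibration. The section 2.3 list (squats, leg press, back extensions, heel raises, single-joint work) contains no jump or cutting movement. It does not name lunges either, but I do not count them because they fit the description of a strength exercise.

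**Step 2: look for wording that reaches the three tasks.**

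- *Familiarity, section 3.1.* Strength exercises only. The experience criterion also refers only to strength training (at least one year, one session or more per week).
- *Familiarity, section 6.2.* The proposed strength exercises only.
- *Injury risk, section 6.2.* The comparator is the participant's usual strength training.
- *Risk category, section 1.5.* It refers to the strength exercises of the intervention. The specific risk attached to motion capture, here and in section 6.2, is skin irritation from markers or devices.
- *Preparation, Table 3.3.3.* A warm-up of 5 to 10 minutes on a rower or bike. No practice of the jump or cutting tasks is described.

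No passage on eligibility or risk mentions jumping, landing or cutting.

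**Step 3: test whether a reading of section 6.2 closes the gap.**

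- *Narrow reading:* the proposed set means the intervention exercises. The three tasks then fall outside both the familiarity safeguard and the risk comparison.
- *Broad reading:* because section 3.3 calls the visit exercises strength training, the proposed set includes Table 3.3.3. Section 6.2 then promises familiarity with jumping and cutting, but the operative criterion in section 3.1 does not ask for it. Section 3.2 says the criteria are clarified by self-declaration, and a participant asked about strength exercises for the knee would have no reason to think of a sprint with a cut.

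On either reading, sections 3.1, 3.3 and 6.2 do not fit Table 3.3.3 and have to be reconciled.

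**The case against.** The strongest reply is that participants are well protected and the fault is loose vocabulary. Sections 3.1 and 3.4 and Table 3.3.3 support much of this:

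- Acute or chronic musculoskeletal pain, surgery within 12 months, ongoing rehabilitation or treatment, and neuromusculoskeletal disease are excluded.
- The criteria are re-checked at both measurement visits, with withdrawal if health has changed.
- Exercise order and 3-minute rests are set to limit fatigue. There is a warm-up, and participants may rest or stop.
- Section 6.2 also says in general that data collection follows standard athlete-monitoring protocols, and that the training routine is discussed. The questionnaire items are not in the documents, so they may already cover jumping or cutting.

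All of this stands, and it rules out saying that participants are unscreened. It does not answer the narrower point. The exclusions concern health, whereas section 6.2 sets its risk comparison beside familiarity, and no written criterion checks familiarity with these tasks. A standard protocol does not show that a given participant has done the movement before.

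A reader might also infer that the results are biased, because a task first met at Visit 2 improves by learning at Visit 3. The documents do not support this as a finding. They do not say which of the six tasks feeds 1RM or the H:Q ratio; the table label and section 2.3 place the tasks and these outcomes under the same heading, but no more. The app's earlier validation (section 1.3) used deadlift, bench press and back squat. No figure gives the size of any learning effect. A shift common to all groups would cancel in the randomised between-group comparison, since the no-training group repeats the same tests. It need not cancel when predicted values are compared with isokinetic values (section 4.1), but that matters only if these tasks are inputs, which is not stated.

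**Conclusion.** The point holds as an inconsistency that bears on participant safety. Three of six visit exercises (50% of the exercise block), scheduled for all 36 participants at two visits, are not covered by the wording of the familiarity criterion or fairly described by the strength-training risk comparison. It should be corrected because the correction is cheap and the risk statement supports the minimal-risk classification.

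The conclusion rests on reading the written criteria as they stand. It assumes nothing about the unseen questionnaire and makes no claim about how many participants are unfamiliar with the tasks; that number is unknown and could be zero.

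Three stronger conclusions should not be drawn:

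- *That these tasks carry the highest knee load of the visit.* The documents give no loading figure for any task, and the same visit includes isokinetic testing.
- *That 36 × 2 × 3 = 216 measures the problem.* It counts planned participant-task-visit combinations, not unfamiliar performances or expected injuries.
- *That the primary analysis is compromised, or that these tasks must be barred as prediction inputs.* Neither follows while their role in 1RM and the H:Q ratio is unstated. No sample-size or error-rate figure changes.

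**What to change.** Reconcile sections 3.1, 3.3 and 6.2 with Table 3.3.3:

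1. In section 3.1, extend the familiarity criterion so that it covers all six visit exercises and names the jump, landing and cutting tasks.
2. Ask about these tasks in the health- and training-related questionnaire already completed at Visit 1, so that the answer is recorded.
3. In section 3.3, stop describing the whole set as strength-training exercises.
4. In section 6.2, confine the comparison with usual strength training to the strength exercises, and address the risk of the jump, landing and cutting tasks in a separate statement. Align section 1.5 if it is meant to cover the visit exercises.

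The cost is one criterion line, one questionnaire item and corrected sentences, submitted under section 5.5 if the change counts as substantial. No visit, measurement or analysis is added. The downside is a slightly narrower recruitment pool, because some people who only do gym strength training would no longer qualify.

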### 3.4 Withdrawal and discontinuation

Participants can withdraw from the study at any time without giving further reasons. A participant can also be withdrawn from the study if she or he does not comply to the instructions of the study personnel as outlined in Table 3.3.3 or the participant's health situation has changed between the initial screening and the training session due to unforeseen circumstances (i.e. exclusion criteria: acute musculoskeletal pain or injury).

If a participant is withdrawn from the study (or withdraws by herself/himself) during the schedule of assessments, only data gathered up to the point of withdrawal will be used for analysis.

All personal data is encrypted by assigning a unique participant ID to all experimental raw data and electronic data sheets, including analysis results. All data is stored on the secured server architecture at the SFSIM with restricted access to study staff only (see also Section 7).

## 4 STATISTICS AND METHODOLOGY

### 4.1. Statistical analysis plan

Statistical analysis will be conducted with SPSS (SPSS v. 21, IBM, USA) after consultation with a statistician in line with previous research by our group.

For the Primary Objective, a repeated measures analysis of variance (ANOVA) will be conducted to assess statistically significant differences between the predicted values of 1RM and H:Q ratio from biomechanical modelling and mobile monitoring with the measured values from optical motion capture and isokinetic strength tests following the 8-week strength training intervention. A correlation analysis will be done to relate the strength-specific outcome parameters to the training-specific parameters for each study group. Principal component and factor analysis will be performed to identify correlations between strength-specific and training-specific parameters.

For validation of the HMF technique, we will follow the statistical methods of previous research by our group [21, 22] to assess the significance in the differences of muscle volume between HMF and MRI, as well as the difference of the predicted adaptation in CSA between HMF and ultrasound. The level of significance in the difference of muscle volume between HMF and MRI is expected to vary across muscle-tendon groups and gender. In particular, no significant differences were found in the predicted volume of semitendinosus and semimembranosus as part of the hamstrings between HMF and MRI in 5 children without CP (MRI 5.1 (0.91) versus HMF 5.0 (0.30) cm^3/kg, p-value >0.05) and in the predicted volume of the quadriceps, including vastus lateralis, medialis, intermedius and rectus femoris, in 6 children with CP (MRI 15.9 (3.20) versus

HMF 16.5 (2.58) cm^3/kg, p-value > 0.05), respectively [22]. It is expected that the accuracy in the predicted muscle volume is improved in the present study by fitting a generic musculoskeletal model to subjects of similar age and gender, and without significant musculoskeletal impairments, as well as additionally considering subject-specific somatotype based on anthropometric measurements. ANOVA will be performed to analyse the pairwise differences in muscle volumes between the HMF and MRI-based results; and to analyse the pairwise differences in the predicted adaptation of hamstrings and quadriceps CSA between HMF and data from ultrasound before and after strength training intervention, respectively. The data from female and male participants will be analysed combined, as well as independently as two different groups.

The level of significance will be set at  $p < 0.05$  for all statistical tests.

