## 2 PROJECT OBJECTIVES AND DESIGN

### 2.1 Hypothesis and primary objective

Hypothesis: It is hypothesized that advanced subject-specific musculoskeletal modelling in combination with mobile monitoring technology as embedded in the iPhone and Apple Watch allow for accurate prediction of changes in muscle strength and muscle size in the lower limbs following an 8-week strength training intervention of key muscle-tendon groups associated with knee joint stability.

Primary Objective: Prediction of changes in muscle strength in the lower limbs due to different strength training volumes by means of the advanced computational modelling, biomechanical analysis and mobile monitoring technology. Of particular interest is the prediction of 1RM and the prediction of the ratio between hamstrings and quadriceps strength (H:Q ratio) compared against isokinetic strength tests as gold standard. Research has clearly shown that the quantification of 1RM is fundamentally important when it comes to the design of safe and efficient resistance training programs. Improved accuracy in the 1RM prediction compared to preliminary studies (i.e. mean %error of 0.27% in 60% and 7.81% in 80% 1RM assessment [29-34]) is expected through the consideration of data from optical motion capture as well as the additional consideration of subject-specific musculoskeletal anatomy from computational modelling.

Secondary Objective: Assessment of changes in muscle size in the lower limbs due to different strength training volumes using the HMF technique. Of particular interest is the prediction of muscle volume using the HMF technique compared against data from MRI as gold standard, as well as the prediction of adaptation in hamstrings and quadriceps CSA due to the strength training intervention using HMF versus data from ultrasound, respectively. Improved accuracies in the assessment of muscle size compared to preliminary studies (i.e. more than 70% accuracy in muscle volume [22]) are expected through the additional data from anthropometric measurements and the matching of generic model to the study-specific population group including gender.

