### 2.2 Primary and secondary endpoints

Primary Endpoint: Changes in muscle strength in the lower limbs following the 8-week strength training intervention of the lower limbs in three study groups with different training volumes. The two strength-specific primary outcome parameters are: 1RM and H:Q ratio. Changes in 1RM and H:Q ratio will be derived using the *iOS Strength Control app* and biomechanical analysis before and after the strength training intervention. Primary outcome parameters will be compared between the three study groups in relation to training volumes (Group#1: no training, Group#2: 1 training per week, Group#3: 3 trainings per week). The accuracy in the prediction of 1RM and H:Q ratio will be compared with data from isokinetic strength tests as gold standard.

Secondary Endpoint: Changes in muscle size of the lower limbs following the 8-week strength training intervention of the lower limbs in three study groups with different training volumes. The two secondary outcome parameters are: muscle volume and CSA. Changes in muscle volume and CSA will be derived using the HMF technique in combination with data from 3D body surface scanning and anthropometric measurements before and after the strength training intervention. Secondary outcome parameters will be compared between the three study groups in relation to training volumes (Group#1: no training, Group#2: 1 training per week, Group#3: 3 trainings per week). The accuracy in the derivation of muscle volume and CSA using the HMF technique will be assessed using data from MRI and ultrasound as gold standard.

Key baseline factors that will likely influence the primary and secondary endpoints are strength training experience and gender. The sample size and population group are specified to allow the analysis of gender-specific differences on study results. Thereby, the inclusion/exclusion criteria and study protocol, including a training-related questionnaire, are defined to minimize the bias of training experience.

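### The primary ANOVA is worded on predicted versus measured values after training and names no factors or deciding term, although the stated aim is to predict change due to training volume

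*Combined protocol and SAP*

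**What the plan says.** The aim is about change. The hypothesis in section 2.1 is that the technology will "allow for accurate prediction of changes in muscle strength and muscle size in the lower limbs following an 8-week strength training intervention". The primary objective is "Prediction of changes in muscle strength in the lower limbs due to different strength training volumes". Section 2.2 defines the primary endpoint in the same way ("Changes in 1RM and H:Q ratio will be derived using the" app and biomechanical analysis, before and after training) and adds that "Primary outcome parameters will be compared between the three study groups in relation to training volumes".

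The primary test in section 4.1 is worded differently: "a repeated measures analysis of variance (ANOVA) will be conducted to assess statistically significant differences between the predicted values of 1RM and H:Q ratio" and the values measured by optical motion capture and "isokinetic strength tests following the 8-week strength training intervention". The sentence mentions neither baseline nor change. It names no within-participant or between-participant factor, no deciding term, and no result that would support the hypothesis. The correlation, principal component and factor analyses that follow do not supply these.

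For the secondary CSA outcome the same section does name change. The ANOVA there is "to analyse the pairwise differences in the predicted adaptation of hamstrings and quadriceps CSA between HMF and data from ultrasound", before and after the intervention.

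**The concern.** A repeated-measures ANOVA with method (predicted, measured), time and possibly group contains several tests that answer different questions. The post-training difference asks whether the level is right at the last visit. The method effect asks whether the level is right on average over both visits. Method-by-time asks whether the mean change is right. Method-by-time-by-group asks whether the effect of training volume on change is right.

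Section 4.1 fixes none of these, and its most literal reading is the first. That test says nothing about whether a gain was detected. If the term is chosen after the data are seen, an app that registers no training gain could be reported as showing no significant difference from the reference. An app that tracks gains well but reads consistently high could be reported as inaccurate.

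**Working it through.** **The plan's own figure.** Section 3.1 gives 11 per group for d = 1.5, power 0.9 and alpha 0.025. The cited squat data give d = (200.8 - 170.6)/√((21.4² + 19.0²)/2) = 30.2/20.24 = 1.49. A two-sample t-test with d = 1.5 needs 10.4, so 11 per group, at one-sided 0.025; two-sided 0.025 needs 12.4, so 13. The stated figure is therefore reproduced with a one-sided 0.025. It concerns a gain in strength, not a prediction error, so it gives no error SD and does not identify a method term.

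**Inputs.** From the documents: 36 complete data sets, 12 per group; p < 0.05 for every test; a 1RM scale of 170.6 kg and a cited gain of 30.2 kg (section 3.1). Assumed, because the documents do not give them: SD s of (predicted - measured) at each visit of 8% of 170.6 kg (range 5-15%); correlation r of the errors between visits of 0 to 0.5; a constant offset of 5%; a mean true gain of 15.1 kg (half of 30.2).

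**Formulas.** Let e2 and e3 be predicted minus measured at Visits 2 and 3.
- Post-value test: mean of e3, SE = s/√36.
- Method effect: mean of (e2 + e3)/2, SE = s√((1 + r)/2)/√36.
- Method-by-time: mean of (e3 - e2), SE = s√(2(1 - r))/√36.

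Rejection rates are exact, from the noncentral t distribution, two-sided 0.05. At 8%, s = 0.08 × 170.6 = 13.65 kg.

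**Case 1: constant offset, change predicted without bias.** The offset is 0.05 × 170.6 = 8.53 kg at both visits. Post-value: 8.53/(13.65/6) = 8.53/2.27 = 3.75 standard errors. Method-by-time: expected value 0.

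**Case 2: the prediction shows no gain, but the post value is right on average.** Errors are +15.1 kg at Visit 2 and 0 at Visit 3. Post-value: expected value 0. Method-by-time with r = 0: 15.1/(19.30/6) = 15.1/3.22 = 4.69 standard errors; with r = 0.5: 15.1/2.27, about 6.6. At SD 15% and r = 0: 15.1/6.03 = 2.50.

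| | Post-value | Method effect | Method-by-time |
|---|---|---|---|
| Case 1, SD 8% | 95% | 99-100% | 5% |
| Case 1, SD 5-15% | 49-100% | 61-100% | 5% |
| Case 2, SD 8% | 5% | 96-99.5% | >99% |
| Case 2, SD 5-15% | 5% | 51-100% | 68-100% |

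The 5% entries do not depend on the assumed SD or correlation, because the quantity tested is zero in those cells.

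**Case 3: the prediction ignores training volume.** Assume true gains of 0, 15.1 and 30.2 kg in Groups 1, 2 and 3, and a predicted gain of 15.1 kg for everyone. Errors in change are +15.1, 0 and -15.1 kg, with mean 0, so method-by-time rejects in about 5%. For method-by-time-by-group (F with 2 and 33 df), the noncentrality is 12 × (15.1² + 0 + 15.1²)/(2s²(1 - r)). At SD 8% this is 5472/372.5 = 14.7 for r = 0 and 29.4 for r = 0.5, giving rejection in 92% and 99.8%. Over SD 5-15% the range is 40-100%.

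**The case against.** Four objections carry weight.

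- **Level accuracy is also a stated aim.** Section 2.1 seeks better 1RM accuracy than preliminary mean errors of 0.27% and 7.81%, and section 2.2 compares the accuracy of 1RM and H:Q ratio with isokinetic tests. A level comparison therefore answers a real question and should be kept. It does not answer the question about change.
- **The post-only reading is not the only one.** The term repeated measures, the before-and-after endpoint in section 2.2 and the matched visits in section 3.3 allow both visits to enter the ANOVA. A reader might infer that the plan commits to a post-value test. It does not: that is the most literal reading of an ambiguous sentence. Adding time still leaves the deciding term unnamed.
- **The sizes rest on assumptions.** The 170.6 kg comes from professional rugby league players, and the offset was chosen. With the plan's own preliminary mean errors as the offset and SD 8%, the post-value test would reject in about 5% (0.27%) or about 100% (7.81%).
- **Case 2 applies one shortfall to all 36, although 12 do not train.** If gains are 0, 15.1 and 30.2 kg by group, the mean shortfall is still 15.1 kg. With group as a factor (33 error df) the overall rates are essentially unchanged.

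A reader might also infer that method-by-time is the only term that matters. The documents do not support that: the objective ties change to training volume, and Case 3 shows method-by-time passing a method that ignores volume.

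**Conclusion.** The concern holds: the target in sections 2.1 and 2.2 is change due to training volume, while the primary test in section 4.1 is worded on values after training and names no factors or deciding term. That the candidate tests can disagree follows from what they measure and needs no assumption. How often they disagree does: 95% against 5% for a 5% offset, and 5% against more than 99% (68-100%) for a missed 15.1 kg gain, under the assumed error SD and correlation. A method that misses the gain could thus pass the literal test about 95% of the time.

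A reader might go on to infer an inflated chance of false success, because several terms are tested at p < 0.05 for two outcomes. The documents do not support that. The hypothesis is accurate prediction, so a significant method term counts against it; a family-wise rate over these terms is the chance of wrongly finding a discrepancy. The hazard here is the free choice of term.

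**What to change.** In section 4.1, replace the primary ANOVA sentence with wording to this effect:

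- For each primary outcome, the change analysis uses the within-participant difference between predicted change (Visit 3 minus Visit 2) and the change measured by isokinetic testing, the gold standard named in sections 2.1 and 2.2, with training group as a factor.
- The mean error in change (method-by-time) is reported overall and by group with 95% confidence intervals, together with the method-by-time-by-group term, which shows whether the effect of training volume is predicted.
- The predicted-versus-measured level comparison at each visit is reported as a separately labelled accuracy analysis.
- A non-significant difference is not read as proof of accuracy. An acceptable error in change, stated in advance, would let the confidence intervals support a conclusion.

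The difference needs both quantities on one scale, so section 4.1 should also say how the isokinetic result is expressed for comparison with 1RM.

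The cost is wording and slightly more analysis. Both visits and all measurements are already scheduled in section 3.3, so no participants or procedures are added. The sponsor gives up the freedom to choose among terms after seeing the data.
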